7.2. Safety Assessments

Refer to the [Schedule Of Activities](#) for time points.

Adverse events will be graded according to the National Cancer Institute Common Terminology Criteria for Adverse Events (NCI CTCAE), version 3.0. Patients are to be followed for adverse events for 28 days after last dose of bosutinib, regardless of causality. Furthermore, all treatment-related adverse events will be followed until Grade ≤ 1 , return to baseline, or in the case of impairment, until the condition stabilizes.

7.2.1. Safety Assessment Methods

Safety will be assessed by physical examination (including vital signs) and laboratory tests (see [Appendix 5](#)), including chest X-ray and ECHO/MUGA scans.

All safety assessments are outlined in the schedule of activity and include adverse event and concomitant medication review, assessment of disease status, PK collection for all eligible patients (except from patients enrolled at sites in China), and ECG monitoring.

7.2.2. Special Recording of Diarrhea Events

EMA has required that ad hoc analyses are conducted in order to evaluate the incidence of diarrhea after study patient's transition to the bosutinib commercial formulation. To satisfy this request, a diarrhea card will be provided to the patients to collect the details of diarrhea events during the first three months on study treatment (see [Appendix 2](#)).

Diarrhea cards will be provided to all patients at the baseline visit. The cards will be collected at the Month 3 study visit; data reported by the patient will be reviewed by the investigator and recorded in the eCRF.

7.2.3. Safety Laboratory Determinations

The investigator will review laboratory test results to determine the occurrence of clinically important abnormalities (ie, AEs). If laboratory values do not return to normal or baseline within a reasonable period, the etiology should be identified and documented appropriately. Only laboratories associated with the investigative site should be used by the investigator for all determinations, unless a special test is required. Every effort should be made by each investigator to designate one primary laboratory for all determinations unless a special test is required. It is the responsibility of site staff to collect valid laboratory certifications and normal ranges for all local laboratories used during the course of the study.

7.2.4. Contraceptive Check

Patients of child-bearing potential will be required to verbally affirm their use of 2 highly effective methods of contraception until at least 28 days after their last dose of bosutinib. This conversation which will be documented in the patient's source records.

7.3. Pharmacokinetics

Steady-state trough concentrations (C_{trough}) of bosutinib will be determined. A total of 1 PK sample per subject will be drawn. All eligible patients (except from patients enrolled at sites in China) will provide a pre-dose blood sample following at least 2 weeks of uninterrupted dosing with bosutinib at the same dose level. This sample will be collected at their first scheduled visit following all appropriate approvals and implementation of protocol amendment # 1. Biological specimen samples for pharmacokinetic analysis must be identified with labels provided by the sponsor. Concentrations of bosutinib will be determined in plasma using a Pfizer -approved and validated liquid chromatography/tandem mass spectrometry (LC/MS/MS) assay.

The objective of the pharmacokinetic analysis is to compare the C_{trough} of bosutinib in this study to C_{trough} of previous studies.

7.3.1. Blood Collections for Plasma PK and BCR-ABL Mutation Analysis

Blood samples (3 mL) to provide approximately 1.0 mL plasma for PK analysis will be collected into appropriately labeled tubes at times specified in the [Schedule Of Activities](#).

One pre dose PK sample per eligible patient will be drawn, to be collected at first occasion after at least 2 weeks of uninterrupted dosing at the same dose level. Actual date and time of treatment dose and PK sampling should be recorded on the eCRF.

Detailed instructions for PK blood sample collection, processing, storage, and shipment will be provided in a lab manual. PK samples must be processed and shipped as indicated in the lab manual to maintain sample integrity. Any deviations from the processing steps (ie, sample collection and processing, interim storage, or shipping conditions), including any actions taken, must be documented and reported to the Sponsor. On a case by case basis, the Sponsor may make a determination as to whether sample integrity has been compromised. Any deviation from the specified sample handling procedure resulting in compromised sample integrity will be considered a protocol deviation.

As part of understanding the PK of the study drug, samples may be used for further characterization and/or evaluation of the bioanalytical method. These data will be used for internal exploratory purposes and will not be included in the clinical report.

BCR-ABL Mutation Analysis

Analysis of the BCR-ABL transcript will be performed using a peripheral blood sample collected at the end-of-treatment visit from each eligible patient in order to identify mutations acquired upon treatment with bosutinib. Mutations will be identified by direct sequencing of the BCR-ABL transcript performed at a Central Laboratory as arranged by the Sponsor. Peripheral blood will be collected and shipped frozen to a central vendor for analysis. Specific instructions for handling and shipment of these samples can be found in Study Reference Manual.

7.3.2. Pregnancy Testing

For female patients of childbearing potential, a serum pregnancy test, with sensitivity of at least 25 mIU/mL, will be performed within 28 days of the first dose of bosutinib at the baseline visit and at the end of treatment visit. Pregnancy tests will also be done whenever one menstrual cycle is missed during the active treatment period (or when potential pregnancy is otherwise suspected), repeated at the end of the study to confirm the patient has not become pregnant during the study. In the case of a positive hCG test, the patient will be withdrawn from study medication but may remain in the study. Pregnancy tests may also be repeated as per request of IRB/IECs or if required by local regulations.

8. ADVERSE EVENT REPORTING

8.1. Requirements

The table below summarizes the requirements for recording safety events on the CRF and for reporting safety events on the Clinical Trial (CT) Serious Adverse Event (SAE) Report Form to Pfizer Safety. These requirements are delineated for 3 types of events: (1) SAEs; (2) non-serious adverse events (AEs); and (3) exposure to the investigational product under study during pregnancy or breastfeeding, and occupational exposure.

Safety Event	Recorded on the CRF	Reported on the CT SAE Report Form to Pfizer Safety Within 24 Hours of Awareness
SAE	All	All
Non-serious AE	All	None
Exposure to the investigational product under study during pregnancy or breastfeeding, and occupational exposure	All (regardless of whether associated with an AE), except occupational exposure	Exposure during pregnancy, exposure via breastfeeding, occupational exposure (regardless of whether associated with an AE)

All observed or volunteered events regardless of] group or suspected causal relationship to the investigational product(s) will be reported as described in the following paragraphs.

Events listed in the table above that require reporting to Pfizer Safety on the CT SAE Report Form within 24 hours of when the investigator becomes aware of the event **All events are to be reported to Pfizer, regardless as to causation.** In the rare situation that the investigator does not become immediately aware of the occurrence of an event, the investigator must report the event within 24 hours and document the time of his/her first awareness of the event. In particular, if the SAE is fatal or life-threatening, notification to Pfizer Safety must be made immediately upon discovery, irrespective of the extent of available event information. This timeframe also applies to additional new (follow-up) information on previously forwarded reports.

For each event, the investigator must pursue and obtain adequate information both to determine the outcome and to assess whether it meets the criteria for classification as an SAE (see the [Serious Adverse Events](#) section below). In addition, the investigator may be requested by Pfizer Safety to obtain specific follow-up information in an expedited fashion. This information is more detailed than that recorded on the CRF. In general, this will include a description of the event in sufficient detail to allow for a complete medical assessment of the case and independent determination of possible causality. Any information relevant to the event, such as concomitant medications and illnesses, must be provided. In the case of a subject death, a summary of available autopsy findings must be submitted as soon as possible to Pfizer Safety. Any pertinent additional information must be reported on the CT SAE Report Form; additional source documents (eg, medical records, CRF, laboratory data) are to be sent to Pfizer Safety **ONLY** upon request.

As part of ongoing safety reviews conducted by the sponsor, any non-serious AE that is determined by the sponsor to be serious will be reported by the sponsor as an SAE. To assist in the determination of case seriousness, further information may be requested from the investigator to provide clarity and understanding of the event in the context of the clinical study.

8.1.1. Additional Details On Recording Adverse Events on the CRF

All events detailed in the table above will be recorded on the AE page(s) of the CRF. It should be noted that the CT SAE Report Form for reporting of SAE information is not the same as the AE page of the CRF. When the same data are collected, the forms must be completed in a consistent manner. AEs should be recorded using concise medical terminology and the same AE term should be used on both the CRF and the CT SAE Report Form for reporting of SAE information.

8.1.2. Eliciting Adverse Event Information

The investigator is to record on the CRF all directly observed AEs and all AEs spontaneously reported by the study subject/[parent(s)/legal guardian/legally acceptable representative]. In addition, each study subject/[parent(s)/legal guardian/legally acceptable representative] will be questioned about the occurrence of AEs in a non-leading manner.

8.1.3. Withdrawal From the Study Due to Adverse Events (see also the [Subject Withdrawal](#) section)

Withdrawal due to AEs should be distinguished from withdrawal due to other causes, according to the definition of AE noted below, and recorded on the CRF.

When a subject withdraws from the study because of an SAE, the SAE must be recorded on the CRF and reported, as appropriate, on the CT SAE Report Form, in accordance with the Requirements section above.

8.1.4. Time Period for Collecting AE/SAE Information

The time period for actively eliciting and collecting AEs and SAEs (“active collection period”) for each subject begins from the time the subject provides informed consent, which is obtained before the subject’s participation in the study (ie, before undergoing any study-related procedure and/or receiving investigational product), through and including a minimum of [28 calendar days; except as indicated below] after the last administration of the investigational product.

For subjects who are screen failures, the active collection period ends when screen failure status is determined.

8.1.4.1. Reporting SAEs to Pfizer Safety

All SAEs occurring in a subject during the active collection period are reported to Pfizer Safety on the CT SAE Report Form.

SAEs occurring in a subject after the active collection period has ended are reported to Pfizer Safety if the investigator becomes aware of them; at a minimum, all SAEs that the investigator believes have at least a reasonable possibility of being related to investigational product must be reported to Pfizer Safety.

Follow up by the investigator continues throughout and after the active collection period and until the event or its sequelae resolve or stabilize at a level acceptable to the investigator, and Pfizer concurs with that assessment.

If a patient begins a new anticancer therapy, SAEs occurring during the above-indicated active collection period must still be reported to Pfizer Safety irrespective of any intervening treatment.

8.1.4.2. Recording Non-serious AEs and SAEs on the CRF

During the active collection period, both non-serious AEs and SAEs are recorded on the CRF.

Follow-up by the investigator may be required until the event or its sequelae resolve or stabilize at a level acceptable to the investigator, and Pfizer concurs with that assessment.

If a patient begins a new anticancer therapy, the recording period for non-serious AEs ends at the time the new treatment is started; however, SAEs must continue to be recorded on the CRF during the above-indicated active collection period.

8.1.5. Causality Assessment

The investigator's assessment of causality must be provided for all AEs (serious and non-serious); the investigator must record the causal relationship on the CRF, and report such an assessment in accordance with the SAE reporting requirements, if applicable. An investigator's causality assessment is the determination of whether there exists a reasonable possibility that the investigational product caused or contributed to an AE; generally the facts (evidence) or arguments to suggest a causal relationship should be provided. If the investigator does not know whether or not the investigational product caused the event, then the event will be handled as "related to investigational product" for reporting purposes, as defined by the sponsor. If the investigator's causality assessment is "unknown but not related" to investigational product, this should be clearly documented on study records.

In addition, if the investigator determines that an SAE is associated with study procedures, the investigator must record this causal relationship in the source documents and CRF, and report such an assessment in the dedicated section of the CT SAE Report Form and in accordance with the SAE reporting requirements.

8.1.6. Sponsor's Reporting Requirements to Regulatory Authorities

AE reporting, including suspected unexpected serious adverse reactions, will be carried out in accordance with applicable local regulations.

8.2. Definitions

8.2.1. Adverse Events

An AE is any untoward medical occurrence in a study subject administered a product or medical device; the event need not necessarily have a causal relationship with the treatment or usage. Examples of AEs include, but are not limited to:

- Abnormal test findings;
- Clinically significant signs and symptoms;
- Changes in physical examination findings;
- Hypersensitivity;
- Progression/worsening of underlying disease
- Drug abuse;
- Drug dependency.

Additionally, AEs may include signs and symptoms resulting from:

- Drug overdose;
- Drug withdrawal;
- Drug misuse;
- Drug interactions;
- Extravasation;
- Exposure during pregnancy (EDP);
- Exposure via breastfeeding;
- Medication error;
- Occupational exposure.

Worsening of signs and symptoms of the malignancy under study should be recorded as AEs in the appropriate section of the CRF. Disease progression assessed by measurement of malignant lesions on radiographs or other methods should not be reported as AEs.

8.2.2. Abnormal Test Findings

Abnormal objective test findings should be recorded as AEs when any of the following conditions are met:

- Test result is associated with accompanying symptoms; and/or
- Test result requires additional diagnostic testing or medical/surgical intervention; and/or
- Test result leads to a change in study dosing (outside of any protocol-specified dose adjustments) or discontinuation from the study, significant additional concomitant drug treatment, or other therapy; and/or
- Test result is considered to be an AE by the investigator or sponsor.

Merely repeating an abnormal test, in the absence of any of the above conditions, does not constitute an AE. Any abnormal test result that is determined to be an error does not require recording as an AE.

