5.2.2. Bosutinib Dose Reduction and Dosing Interruptions

As in the parent studies, the bosutinib dose can be reduced and/or dosing interrupted in case of treatment-related toxicity according to the guidelines described in the following tables.

Table 3. Non Hematologic Treatment Related Toxicity

Adverse Event	Action
Grade 1	Remain on current dose level
Grade 2	For persistent, clinically relevant toxicity not responding to optimal management: Interrupt bosutinib, then reintroduce at the same dose or reduce dose by one level upon recovery to Grade ≤ 1 within 4 weeks of stopping treatment.
Grade 3 ^a	For persistent, clinically relevant toxicity not responding to optimal management: Interrupt bosutinib, then dose reduce by 1 level upon recovery to Grade ≤ 1 within 4 weeks of stopping treatment. If recovery takes longer than 4 weeks, the investigator should contact the sponsor to determine if the patient may continue on bosutinib.
Grade 4 ^a	Interrupt bosutinib. Investigator and sponsor to determine if patient may continue on bosutinib with appropriate dose reduction.

a. For patients who have required a dose reduction due to toxicity, but then have been free of the specific toxicity (Grade ≤ 1) for at least 1 month and are otherwise tolerating bosutinib well, the investigator may choose to re-escalate the dose by one dose level each month (ie, increase the daily dose by 100 mg/month) until the patient is back to the starting or previous dose (whichever is higher). See [Table 2](#) for available dose levels.

Table 4. Hematologic Treatment Related Toxicity

Adverse Event	Action
Grade 1	Remain on current dose level
Grade 2	Remain on current dose level
Grade 3 ^a	First episode: Interrupt bosutinib until recovery to Grade ≤ 2 . If patient recovers within 2 weeks of treatment hold: re-introduce bosutinib at same dose. If patient recovers within 4 weeks of treatment hold: reduce bosutinib by one dose level. Additional episodes: Interrupt bosutinib until recovery to Grade ≤ 2 and then reduce bosutinib by one dose level. In both cases, if recovery takes longer than 4 weeks, the investigator should contact the sponsor to determine if the patient may continue bosutinib.
Grade 4 ^a	Withhold bosutinib. Investigator and sponsor to determine if patient may continue bosutinib with appropriate dose reduction.

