6.4. Long-Term Follow-up Visit

Patients who discontinue treatment with bosutinib prior to the end of the study will enter into the Long-Term Follow-Up period. Patients will be followed for the duration of study in order to assess the survival status of the patient. Details of any subsequent therapy with TKIs or other anti-cancer therapy and response following bosutinib discontinuation will be collected on LTFU patients if available.

Follow-up will be conducted every 3 months from the last dose of bosutinib. Information will be collected via clinical visit or telephone contact

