6.2.7. Adverse Events of Special Interest

Adverse events including ALT, AST, thrombocytopenia (including MedDRA preferred term [PT] Platelet Count Decreased), neutropenia (including PT Neutrophil Count Decreased), anemia (including PT Hemoglobin Decreased), diarrhea, nausea, vomiting, cardiac toxicity (definition to be determined before DBL), vascular toxicity (definition to be determined before DBL), and renal toxicity (definition to be determined before DBL) will be summarized. Additional AEs or AE clusters may be summarized if deemed appropriate. AE characteristics to be summarized include maximum toxicity, time to first event, duration of any grade event, cumulative duration of grade 3/4 events, and successful rechallenge (those patients who were re-dosed and did not discontinue bosutinib due to this AE after having a dose delay).

The diarrhea characteristics will also be summarized separately for data from B1871008 and B1871006 compared to B1871040 in order to assess the impact of changing to the clinical formulation of bosutinib from the parent studies to the commercial formation in this study. For ongoing events at the time of the switch to commercial formulation, the stop date for the event attributed to the clinical formulation will be set to date of the start of commercial formulation minus one and the start date for the event attributed to the commercial formulation will be set to the start date of commercial formulation.

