8.2.2.2. Treatment and Compliance

Descriptive statistics for continuous exposure variables treatment duration and cumulative received dose, and received dose over time (% receiving 600, 500, 400, 300, 200, or 0 mg at specific time points) will be calculated.

The number and percentage of patients with at least one dose reduction due to AE, dose delay due to AE, and escalation to 600 mg will be summarized. The number and percentage of patients who experienced more than 1 event will also be summarized.

The number and percentage for reasons for treatment discontinuation will be summarized and listed. A listing of COVID-19 related treatment discontinuations will be provided.

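### Protocol 8.2.2 does not require an AE record for a laboratory toxicity held or dose-reduced exactly per Tables 3 and 4, so AE-linked dose-change and rechallenge summaries may be incomplete

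*Protocol*

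**What the plan says.** **Recording rule.** Protocol 8.2.2 states: "Abnormal objective test findings should be recorded as AEs when any of the following conditions are met". The four conditions are, in short: accompanying symptoms; further diagnostic testing or intervention; a consequence for dosing, study participation or treatment; and judgement. The third contains "Test result leads to a change in study dosing (outside of any protocol-specified dose adjustments) or discontinuation from the study". The fourth is "Test result is considered to be an AE by the investigator or sponsor". The section adds: "Merely repeating an abnormal test, in the absence of any of the above conditions, does not constitute an AE".

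**Dosing rules.** Protocol 5.2.2, Tables 3 and 4, set interruptions and reductions by toxicity grade, and both tables head the triggering column Adverse Event. For Grade 3 hematologic toxicity, Table 4 begins "First episode: Interrupt bosutinib until recovery to Grade" 2 or lower.

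**Other text on laboratory findings.** Protocol 7.2.3 treats clinically important laboratory abnormalities as AEs. Protocol 8.2.1 lists abnormal test findings among its examples of AEs.

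**Outputs.** SAP 8.2.2.7 tabulates treatment-emergent AEs that led to dose delays or reductions, and AEs that led to stopping treatment. SAP 8.2.2.8 summarises successful rechallenge for eight AEs. SAP 6.2.7 defines it as "those patients who were re-dosed and did not discontinue bosutinib due to this AE after having a dose delay". SAP 8.2.2.2 counts "patients with at least one dose reduction due to AE, dose delay due to AE, and escalation to 600 mg".

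**The concern.** In this trial, dose changes for laboratory toxicity are largely the ones the protocol itself prescribes. The parenthesis therefore removes the dosing trigger in the cases where it would most often apply. Section 8.2.2 says such a dose change is not in itself a reason to record an AE, while Tables 3 and 4 already call the triggering finding one. Two sites can each follow the protocol and record the same Grade 3 neutropenia differently.

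Long-term safety is an endpoint for all patients (Protocol 2.2), and laboratory toxicity is common with this drug. In B1871008, 66% of bosutinib patients had interruptions and 43% had reductions. Grade 3-4 rates were 23% for ALT, 12% for AST, 14% for thrombocytopenia, 10% for neutropenia and 8% for anemia (Protocol 1.2.2). Those are rates in newly treated patients, so they show relevance and not the rate to expect among long-term continuers. Five of the eight AEs with a planned rechallenge summary are laboratory events.

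**Working it through.** The plan states no figure for this point, so the check is mainly a comparison of texts.

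**1. Is the hold a protocol-specified adjustment?** Yes. Table 4 prescribes interruption for a first Grade 3 hematologic toxicity, and a same-dose restart or a one-level reduction depending on recovery time. Table 3 does the same for persistent, clinically relevant Grade 2 or 3 non-hematologic toxicity. Such a change lies inside the parenthesis.

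**2. Does another condition capture it?** Take a symptom-free Grade 3 neutropenia, held per Table 4 with no added treatment.
- Symptoms: none, by construction.
- Further testing or intervention: following counts to recovery is repeat testing, which 8.2.2 says is not enough alone.
- Added treatment: none, by construction.
- Judgement: available, and decisive.

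**3. Which outputs need the AE record?**
- SAP 8.2.2.7 (AEs leading to delays or reductions): yes.
- SAP 6.2.7 and 8.2.2.8 (rechallenge): yes, because the definition runs through the AE.
- SAP 8.2.2.2 (reductions and delays due to AE): unclear. Reasons for dose modification are a separate exposure endpoint (SAP 6.2.1), so this count may come from the dosing record.
- SAP 6.2.3 and 8.2.2.4 (maximum grade, time to first event, duration, cumulative Grade 3/4 duration): no, these use laboratory values. They carry no dosing action.

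**4. Parent-study figures.** With 570 patients in B1871006, AEs leading to discontinuation reproduce as 26/570 = 4.6% (thrombocytopenia), 11/570 = 1.9% (ALT increased) and 8/570 = 1.4% (neutropenia), matching Protocol 1.2.2. Such events were AE-coded there, but the parent studies' recording rule is not in the documents.

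**5. Direction for rechallenge.** Assume true success is 80% (borrowed from the transaminase rechallenge result in Protocol 1.2.2) and that the denominator is patients with a recorded AE and a delay.
- A share u of successes is unrecorded, all failures recorded: apparent success = 0.80(1 - u) / [0.80(1 - u) + 0.20]. For u = 10%, 25%, 50%: 0.72/0.92 = 78%, 0.60/0.80 = 75%, 0.40/0.60 = 67%.
- A share v of failures is unrecorded, all successes recorded: apparent success = 0.80 / [0.80 + 0.20(1 - v)]. For v = 10%, 25%, 50%: 0.80/0.98 = 82%, 0.80/0.95 = 84%, 0.80/0.90 = 89%.

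The bias has no fixed sign.

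**6. Illustration of size, on assumed inputs only.** Let f be the share of extension dose delays that are laboratory-driven and r the share of those that still get an AE record. Captured share = (1 - f) + f r.
- f = 0.3, r = 0.75: 0.70 + 0.225 = 0.925.
- f = 0.5, r = 0.5: 0.50 + 0.25 = 0.75.
- f = 0.7, r = 0.25: 0.30 + 0.175 = 0.475.

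That describes extension delays. The SAP pools parent and extension data, so a patient with an AE-linked delay already counted in the parent study is not lost from an overall at-least-one count. If 5-15% of patients had their first delay in the extension (assumed), the pooled count falls by between 0.05 x 0.075 = 0.4 and 0.15 x 0.525 = 7.9 percentage points. At the midpoint loss of 25% the fall is 1.3 to 3.8 points.

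**The case against.** The strongest reply is that 8.2.2 bars nothing. It narrows one of four alternative triggers. Protocol 7.2.3 and 8.2.1 both point towards recording, and Protocol 6.1 says baseline abnormalities are to be managed as AEs under Sections 5.2 and 5.3. An investigator who applies Tables 3 or 4 has already graded the finding and judged it treatment-related; Table 3 holds at Grades 2 and 3 also require clinical relevance. Calling it an AE under the judgement condition is then the natural step. Grade 4 events and slow recoveries go to the sponsor in any case.

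Much of this stands. A reader might infer that 8.2.2 exempts these toxicities from AE recording, or that they vanish from the safety report. The documents support neither: recording remains open, and the laboratory summaries keep incidence, grade and duration. What the reply does not remove is that recording depends on judgement while the outputs assume it happened. Clinical importance is left undefined in 7.2.3, and a first Grade 3 cytopenia under Table 4 carries no clinical-relevance test.

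On permanent stops, the reply is that discontinuation from the study is a trigger outside the parenthesis, and Protocol 6.5 discusses study withdrawal and stopping bosutinib together. Against that, Protocol 6.4 says: "Patients who discontinue treatment with bosutinib prior to the end of the study will enter into the Long-Term Follow-Up period". Stopping treatment is thus not leaving the study, whereas the SAP reports treatment discontinuations. The mismatch is real but is a weaker, secondary point, since sites may read the phrase broadly.

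**Conclusion.** The concern holds in a limited form. A symptom-free laboratory toxicity held or reduced exactly per Tables 3 and 4 meets no mandatory AE-recording condition in Protocol 8.2.2. The extension contribution to the AE-linked delay and reduction tables, and to rechallenge for the five laboratory AEs, can therefore be incomplete and vary by site. What is at risk is the link between toxicity and dosing action.

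Any under-recording makes the AE-linked counts too low. A reader might go further and infer a general bias towards better tolerability, or take the captured share of 48-93% as an estimate. Neither is supported: the rechallenge percentage can move either way, and the range comes entirely from assumed inputs. The true loss cannot be derived from the documents. The conclusion assumes that SAP 8.2.2.7 and 8.2.2.8 are built from AE records, as their wording implies; SAP 8.2.2.2 may be less affected. This should be corrected, and it does not undermine the laboratory safety summaries.

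**What to change.** **Protocol 8.2.2.** Reconcile the section with Tables 3 and 4 and with 7.2.3. Delete the parenthesis in the third condition, and extend its discontinuation wording to cover discontinuation of bosutinib as well as discontinuation from the study. Any test result that leads to interruption, reduction or permanent stop of bosutinib is then recorded as an AE. No dosing rule changes.

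**SAP 8.2.2.2, 8.2.2.7 and 8.2.2.8, for data already collected.** Add a supplementary count of dose delays, reductions and stops whose recorded dose-modification reason (SAP 6.2.1) is a laboratory toxicity, reported beside the AE-based count. Do not attribute a dose change to laboratory toxicity merely because it coincides with a laboratory grade: without a time window and an attribution rule, that would sweep in unrelated holds. State which source feeds the due-to-AE counts in SAP 8.2.2.2.

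**Cost.** Two wording changes, one supplementary derivation, some additional AE records, and slightly less favourable AE-related dose-change rates. The supplementary count depends on the dosing record giving a specific enough reason, which the documents do not show.
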